### Maintenance Phase

Subjects who experience a severe EGE flare and/or worsening of EGE symptoms (for 2 consecutive visits [4 weeks apart], described in [Section 6.4.2.10](#)) at the beginning of or during the Maintenance Phase will need to discontinue participation in the Maintenance Phase and may be eligible to enter the OLE Phase at the ET Visit.

If the gastric/duodenal eos count is required to determine the need for emergent rescue therapy during the Maintenance Phase, the results of the gastric/duodenal eos count will be disclosed as long as the investigator requires the result. The subject may also be eligible to enter the OLE Phase.

Subjects experiencing a mild to moderate EGE flare in the Maintenance Phase will continue the study and will be eligible to enter the OLE Phase following the completion of the Week 48 Visit.

### OLE Phase

During the OLE Phase, subjects who demonstrate a persistent lack of improvement, worsening of EGE symptoms or severe EGE flare should be evaluated if continuation of study treatment is appropriate. While subjects will have the opportunity to continue participation in the OLE Phase with use of rescue therapy as needed, based on clinical judgment, the investigator should discontinue any subject if study participation no longer is in the best interest of the subject. Subjects who are discontinued from the OLE Phase will be asked to complete an OLE-ET/EoT Visit ([Section 6.2.2](#)) and the two Safety Follow-up Visits ([Section 6.3.1](#)).

## **3.2 Study Duration for Subjects**

The maximum duration of subject participation in the Screening Period, Induction Phase and Maintenance Phase is approximately 72 weeks, including the Interim and the Final Safety Follow-up Visits. Subjects will participate for up to 4 weeks in the Screening Period (the screening EGD may be completed up to 8 weeks prior to Day 1), 16 weeks in the Induction Phase, and 32 weeks in the Maintenance Phase of the study. Subjects completing the Maintenance Phase who do not continue IP administration in the OLE Phase will complete the Interim and the Final Safety Follow-up Visits (at 8 and 16 weeks) after final IP administration.

Subjects who enter the OLE Phase will complete the OLE baseline assessments on Day 1, excluding those obtained from either the Induction Phase Week 16 Visit, the Maintenance Phase Week 48 Visit, or the ET Visit during the Maintenance Phase, as applicable. Subjects will receive weekly doses of IP during the OLE Phase for a minimum duration of 2 years and will complete an OLE-ET Visit or an OLE-EoT Visit within 2 weeks after the final dose and an Interim and a Final Safety Follow-up Visits at 8 and 16 weeks, respectively, after the final dose. Individual subject participation in the OLE Phase may be a minimum of 2 years but may extend for a longer duration, provided the subject does not withdraw from the OLE Phase prior to Year 2 of the OLE.

Subjects may continue participation to the OLE Phase as long as they tolerate treatment and are receiving benefit from participation in the study. Participation may continue until the marketing launch (the terms “this study” in this protocol will automatically be replaced with “post-marketing clinical study” on and after the date of marketing approval in Japan), or the subject decides to

withdraw from the study, the investigator decides to withdraw the subject from the study, or the Sponsor decides to terminate the study (see [Section 12.8](#)).

### **3.3 End of Trial**

The End of Trial is defined as either the date of the last visit of the last subject to complete the post-treatment follow-up (the Final Safety Follow-up Visit), or the date of receipt of the last data point from the last subject that is required for primary, secondary [REDACTED] analysis, as prespecified in the protocol, whichever is the later date.

## 4 STUDY POPULATION

### 4.1 Number of Subjects

The study population will consist of males and females aged 12 to 75 years (inclusive) with EGE. Forty-five adults (aged 18 to 75 years) and adolescents (aged 12 to 17 years) will be enrolled in the study.

### 4.2 Inclusion Criteria

Subjects must satisfy the following criteria to be enrolled in the study:

1. Subject must be  $\geq 12$  years and  $\leq 75$  years of age and have a body weight of  $\geq 30$  kg at the time of signing the informed consent form (ICF).  
If a subject is  $< 18$  years old, subject assent must be obtained and parental/legal representative consent is required.
2. Subjects who were diagnosed with EGE at least 3 months prior to study entry
3. Subject has histologic evidence of EGE defined as  $\geq 30$  eos/hpf in at least 5 hpf in the stomach and/or  $\geq 30$  eos/hpf in at least 3 hpf in the duodenum while on stable background therapy (eg, corticosteroids, however a stable dose of prednisone [up to 10 mg/day] is allowed, see Exclusion Criterion 9) for EGE. The histologic criterion for diagnosis of EGE must be confirmed by a centrally read histological assessment of an EGD specimen during the Screening Period prior to randomization.
4. Subject has weekly symptom scores of  $\geq 4/15$  for any of Gastric Pain Symptoms domain, Stomach Heaviness Symptom domains, and /or Diarrhea Symptoms domain as assessed by the Izumo Scale with electronic device for the 2 consecutive weeks before the IP administration on Day 1.
5. Subjects must agree to maintain a stable diet (including any food elimination diet for the treatment of food allergy or EGE) from the first Screening Visit and throughout the duration of the study, and subjects must have maintained a stable diet for at least 4 weeks prior to the first Screening Visit. Subjects must agree not to introduce any changes in their diet while participating in the study. If the subject is currently successfully treated for EGE with dietary modifications (eg, food elimination diet) and resulting in a complete response to EGE, the subject is not allowed to participate to this study.
6. Subjects currently receiving systemic corticosteroids, inhaled corticosteroids, proton pump inhibitors (PPIs), leukotriene receptor antagonists (eg, montelukast), or mast cell stabilizers (eg, cromolyn sodium) for indications of EGE or other than EGE, or medium potency topical corticosteroids (eg, mometasone furoate cream or lotion) for dermatologic conditions, must maintain stable doses/regimens for at least 4 weeks prior to the first Screening Visit and regimens must remain stable throughout the duration of the study except for systemic corticosteroids (the dose/regimen of systemic corticosteroids must remain stable for the 16 weeks of the Induction Phase). If recently discontinued, the medication must have been discontinued at least 4 weeks prior to the first Screening Visit.
7. Female subjects of childbearing potential must agree to practice a highly effective method of contraception. Highly effective methods of contraception are those that alone or in combination result in a failure rate of a Pearl index of less than 1% per year when used consistently and correctly.

An FCBP is a female who: 1) has achieved menarche at some point; and 2) has not undergone

a hysterectomy, bilateral oophorectomy, or bilateral salpingectomy; or 3) has not been naturally postmenopausal (amenorrhea following cancer therapy does not rule out childbearing potential) for at least 24 consecutive months (ie, has had menses at any time in the preceding 24 consecutive months). An FCBP must follow the criteria below:

- a. Have 2 negative pregnancy tests as verified by the investigator prior to starting study therapy. She must agree to ongoing pregnancy testing during the course of the study and through the Final 16-week Safety Follow-up Visit. This applies even if the subject practices true abstinence\* from heterosexual contact.
- b. Either commit to true abstinence\* from heterosexual contact (which must be reviewed on a monthly basis and source documented) or agree to use, and be able to comply with, highly effective contraception without interruption throughout the study and for 5 months after the last dose of IP. Acceptable methods of birth control in this study are the following (birth control must be effective by the time the FCBP subject is randomized into the study [eg, hormonal contraception should be initiated at least 28 days before randomization]):
  - combined hormonal (estrogen and progestogen containing) contraception, which may be oral, intravaginal, or transdermal  
Note: intravaginal and transdermal combined hormonal contraception are not approved in Japan.
  - progestogen-only hormonal contraception associated with inhibition of ovulation, which may be oral, injectable, or implantable  
Note: progestogen-only hormonal contraception is not approved in Japan.
  - placement of an intrauterine device (IUD)
  - placement of an intrauterine hormone-releasing system (IUS)
  - bilateral tubal ligation; or bilateral tubal occlusion (if an implantable device was recently placed, the subject must use an additional effective method of birth control until full occlusion has been confirmed and documented)
  - vasectomized partner (vasectomized partner is a highly effective birth control method provided that the partner is the sole sexual partner of the FCBP and has received medical assessment of the surgical success)
  - sexual abstinence

8. Subject is willing to receive weekly SC injections throughout the study.
9. Subject must understand and voluntarily sign an ICF prior to any study-related assessments/procedures being conducted.
10. Subject is willing and able to adhere to the study visit schedule and other protocol requirements.

---

\* True abstinence is acceptable when this is the preferred and usual lifestyle of the subject. Periodic abstinence (eg, calendar, ovulation, symptothermal, post-ovulation methods), withdrawal (coitus interruptus), and lactational amenorrhea method are not acceptable methods of contraception.

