g For females of childbearing potential (FCBPs), urine (or serum) pregnancy test will be performed at OLE Day 1/Baseline and urine pregnancy tests will be done at subsequent visits. In the event of a positive urine test, the subject is not to be dosed, and confirmation with a serum pregnancy test should be performed. At each study visit, the investigator will counsel FCBP subjects on pregnancy precautions for the duration of the study.

h Complete physical examination is to be performed at OLE Day 1/Baseline, OLE Week 24, OLE Week 48, at the Quarterly 4 Visit, at the OLE-ET/EoT Visit, and at the 2 Safety Follow-up Visits; abbreviated physical examination is to be performed at OLE Week 4, Week 8, Week 16, Week 36, and at the Quarterly 1, 2, and 3 Visits.

i [REDACTED] OLE Week 24, OLE Week 48, OLE Q4 Visits (OLE Year 2 and beyond), the EGE Flare Assessment Visit and OLE-ET/EoT Visit in which the EGID severity scoring is scheduled.

j If anti-drug antibodies (ADAs) are detected, they will be further characterized as to whether the ADAs are neutralizing or not in nature.

x All subjects will receive weekly open-label CC-93538 360 mg during the OLE Phase. Subjects will be given their first dose of CC-93538 at the OLE Day 1 Visit (which could be the same day as the Induction Phase Week 16, the Maintenance Phase Week 48, or ET Visit during the Maintenance Phase). Subjects will then receive weekly doses throughout the OLE Phase for as long as the study is active; participation may continue until the subject decides to withdraw from the study, the investigator decides to withdraw the subject from the study, or the Sponsor decides to terminate/complete the study. The first 3 weekly SC doses (OLE Day 1, Week 1, and Week 2) will be required to be given in the clinic, and subjects will remain in the clinic for at least 30 minutes following dosing for observation. Additionally, the investigator will review the importance of IP compliance and evaluate compliance for each subject in accordance with the protocol. To ensure accurate dose administration and compliance with the new single 2 mL weekly SC injection using the 360 mg/2 mL [redacted] presentation, after the new 360 mg/2 mL [redacted] presentation is introduced into the OLE Phase for subjects who did not begin dosing with

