### 6.3 Follow-up Period

#### 6.3.1 Safety Follow-up (Interim 8-week and Final 16-week)

All subjects will be followed for 16 weeks after the last dose of IP or until the Final Safety Follow-up Visit, whichever is longer, for AE reporting, as well as SAEs made known to the investigator at any time thereafter that are suspected of being related to IP, as described in [Section 10.2.3](#).

In the Induction Phase, subjects who discontinue from the study prior to completing Week 16, or subjects who complete Week 16 and do not enter the Maintenance Phase or the OLE Phase will return for an Interim and a Final Safety Follow-up Visit at 8 and 16 weeks, respectively, after final IP administration (at Week 23 and Week 31 for subjects completing the Induction Phase) for the assessment of safety and clinical status after exiting the study. However, subjects who are permanently discontinued from IP and continue study participation in order to complete safety and efficacy assessments in the phase of the study that permanent discontinuation from IP occurs (according to [Section 11.1](#)) will return for the Interim and Final Safety Follow-up Visits 8 and 16 weeks after their last study visit instead of their last dose of IP (eg, Week 16 or the ET Visit). Assessments should be performed in accordance with the Table of Events ([Table 4](#)). Subjects who continue participation in the Maintenance Phase or the OLE Phase will not return for the 2 Safety Follow-up Visits.

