Telephone call reminders may take place before the 28-day collection period for daily assessment preceding the OLE Week 24, OLE Week 36 and OLE Week 48 endpoint assessments (ie, just prior to OLE Weeks 20, 32 and 44), if applicable. A telephone contact may be made at other time points as part of ongoing surveillance.

Refer to [Section 6.4](#) for a description of the efficacy assessments conducted throughout the study.

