All subjects will be monitored for AEs, including AEs related to SARS-CoV-2 infection, during the study. Assessments may include monitoring of any or all of the following parameters: the subject's clinical symptoms, laboratory, pathological, radiological or surgical findings, physical examination findings, or findings from other tests and/or procedures. In addition, /PFS device failures or malfunctions should be captured during the study, and any device-related AEs should also be documented. Each study visit will include an assessment for AEs, and subjects who develop an intercurrent illness between study visits are encouraged to contact the investigator, who will determine if a clinical assessment is required. In addition, AEs or SAEs related to SARS-CoV-2 infection will also trigger additional data collection through specialized eCRF pages, which will allow the Sponsor to further evaluate these events.

All AEs, including AEs related to SARS-CoV-2 infection, will be recorded by the investigator from the time the subject signs informed consent/assent until 16 weeks after the last dose of IP or the final 16-week Safety Follow-up Visit, whichever is longer, as well as those SAEs made known to the investigator at any time thereafter that are suspected of being related to IP. AEs and SAEs will be recorded on the AE page of the eCRF and in the subject's source documents. Refer to [Section 10.5](#) for instructions on how to report SAE to Drug Safety.

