### **10.4.1    *Females of Childbearing Potential***

Pregnancies and suspected pregnancies (including elevated  $\beta$ -hCG or positive pregnancy test in a female subject of childbearing potential regardless of disease state) occurring while the subject is on IP, or within 5 months of the subject's last dose of IP, are considered immediately reportable events. Investigational product is to be discontinued immediately and the subject instructed to return any unused portion of the IP to the investigator. The pregnancy, suspected pregnancy, or positive pregnancy test must be reported to Celgene Drug Safety immediately by email, phone or facsimile, or other appropriate method, using the Pregnancy Initial Report Form, or approved equivalent form.

The female subject may be referred to an obstetrician-gynecologist or another appropriate healthcare professional for further evaluation.

The investigator will follow the female subject until completion of the pregnancy, and must notify Celgene Drug Safety immediately about the outcome of the pregnancy (either normal or abnormal outcome) using the Pregnancy Follow-up Report Form, or approved equivalent form.

If the outcome of the pregnancy was abnormal (eg, spontaneous abortion), the investigator should report the abnormal outcome as an AE. If the abnormal outcome meets any of the serious criteria, it must be reported as an SAE to Celgene Drug Safety by facsimile, or other appropriate method, within 24 hours of the investigator's knowledge of the event using the SAE Report Form, or approved equivalent form.

All neonatal deaths that occur within 28 days of birth should be reported, without regard to causality, as an SAE. In addition, any infant death after 28 days that the investigator suspects is related to the in utero exposure to the IP should also be reported to Celgene Drug Safety by

facsimile, or other appropriate method, within 24 hours of the investigator's knowledge of the event using the SAE Report Form, or approved equivalent form.

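### The plan sets a 5-month contraception and pregnancy-reporting window after the last dose, but scheduled testing and contact for most women of childbearing potential end at 16 weeks (minor)

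*Combined protocol and SAP*

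**What the plan says.** Section 4.2, criterion 7b, requires FCBP to commit either to true abstinence, reviewed monthly and source documented, or to "highly effective contraception without interruption throughout the study and for 5 months after the last dose of IP". Section 10.4.1 uses the same horizon for reporting: pregnancies and suspected pregnancies "occurring while the subject is on IP, or within 5 months of the subject's last dose of IP, are considered immediately reportable events".

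The scheduled contacts stop sooner:

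- **Testing.** Criterion 7a: "She must agree to ongoing pregnancy testing during the course of the study and through the Final 16-week Safety Follow-up Visit".
- **Follow-up.** Section 6.3.1: "All subjects will be followed for 16 weeks after the last dose of IP or until the Final Safety Follow-up Visit, whichever is longer".
- **Adverse event recording.** Section 10.1 runs from consent "until 16 weeks after the last dose of IP or the final 16-week Safety Follow-up Visit, whichever is longer". Later events are accepted only as suspected-related SAEs that become known to the investigator.
- **Counselling.** It is tied to visits (Table 4, footnote k; likewise Tables 5 and 6, footnote g): "At each study visit, the investigator will counsel FCBP subjects on pregnancy precautions for the duration of the study".
- **Telephone contact.** Sections 6.2 and 6.3.2 carry the same permissive sentence: "A telephone contact may be made at other time points as part of ongoing surveillance". Neither schedules a call after the Final Safety Follow-up Visit.

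Tables 4, 5 and 6 show no visit after that one.

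**The concern.** The sponsor decided that pregnancy matters for 5 months after the last dose. It asks women to prevent it for that long and asks investigators to report it at once. An investigator can report only what is known, and the last scheduled occasion for learning of a pregnancy comes at about three quarters of the window. A pregnancy that begins or is first recognised after that could go unrecorded, and the follow-up to outcome that Section 10.4.1 requires would not start. What is at stake is subject safety and the completeness of pregnancy data for a new antibody. Sample size, power, type I error and the efficacy endpoints are unaffected.

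**Working it through.** **1. Reproduce the plan's 16 weeks.** Dosing day = 7 × week + 1.
- Induction: last dose Week 15 = Day 106; Final visit Week 31 = Day 218 (Table 4). 218 − 106 = 112 days.
- Maintenance: last dose Week 47 = Day 330; Final visit Week 63 = Day 442 (Table 5). 442 − 330 = 112 days.
- Extension: 16 weeks after the final dose (Table 6). 16 × 7 = 112 days.

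All three agree with the stated 16 weeks. The visit window is ±7 days, so the visit falls on Days 105 to 119 after the last dose.

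**2. Length of the reporting window.** Adding 5 calendar months to every start date over two years gives 150 to 153 days.

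**3. Gap = 5 months − day of the Final visit.**
- Nominal: 150 − 112 = 38; 153 − 112 = 41 days.
- With the visit window: 150 − 119 = 31; 153 − 105 = 48 days.
- Nominal share of the window: 38/150 = 25.3%; 41/153 = 26.8%.

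**4. Subjects who stop treatment but stay in the phase.** Section 6.3.1 then counts the 16 weeks from the last study visit. For last dose at week w and last visit at Week 16 or 48, nominal days covered = (16 + 16 − w) × 7 or (48 + 16 − w) × 7.
- w = 10 or 42: 154 days, no gap. Earlier last doses also leave none.
- w = 12 or 44: 140 days, gap 10 to 13 days.
- w = 15 or 47: 119 days, gap 31 to 34 days.

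In the extension, stopping treatment means leaving the study (Section 11.1), so this relief does not apply.

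**5. Pharmacokinetics.** Five half-lives, and fraction left at Day 112 = 2^(−112/half-life):
- RPC02-1901 (360 mg, 150 mg/mL), 475 to 497 hours: 5 × 475/24 = 99 days; 5 × 497/24 = 104 days; 2.0% to 2.4% left.
- CC-93538-CP-001, 18.7 to 23.4 days: 93.5 to 117 days; 1.6% to 3.6% left.
- M10-378, upper value 26.7 days: 133.5 days; 5.5% left.

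Day 112 falls short of five half-lives only for half-lives above 112/5 = 22.4 days.

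**6. Expected pregnancies in the gap.** The number of FCBP is not given. As an extreme, take all 45 subjects and the longest nominal gap: 45 × 41/365 = 5.1 woman-years. Criterion 7 requires methods with a failure rate below 1% per year, so the expected number is below 5.1 × 0.01 = about 0.05.

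**The case against.** The strongest reply is that nothing here is contradictory. Criterion 7a limits scheduled testing, 7b governs the subject's behaviour and 10.4.1 sets a duty to report. A duty can outlast the visits, as it does for late suspected-related SAEs. That stands: no rule breaks another, and what is missing is a planned way of finding out.

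A reader might infer that all follow-up ends at 16 weeks. The documents do not support this. Unresolved SAEs are followed to recovery or death (Section 10.2.6), a known pregnancy is followed to completion (Section 10.4.1), and subjects who stop treatment but stay in Induction or Maintenance are followed from their last study visit. Nor, for that last reason, does the gap affect every woman who stops treatment.

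A reader might also infer that the uncovered weeks carry meaningful drug exposure. The data are mixed. The study of this dose and formulation puts five half-lives before even the earliest Final visit; only the upper values from two other Phase 1 studies go past Day 112. The 5-half-life rule in exclusion criteria 8 and 12 is an entry washout for other drugs, not a standard for fetal exposure. The case rests on the sponsor's own choice of 5 months.

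The monthly abstinence review in 7b could be read as running to month 5, which would give abstinent women a contact. The grammar is ambiguous, and the reading would not help women using contraception. The optional calls schedule nothing. The consent form is not available and may ask subjects to report a late pregnancy, but that would still be self-report.

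**Conclusion.** The mismatch holds, at minor severity. For FCBP who complete Induction or Maintenance without continuing, who leave when treatment stops, or who stop in the extension, 38 to 41 days of a 150-to-153-day reporting window have no scheduled visit, test or call. The range is 31 to 48 days once visit timing is allowed for.

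This assumes that 5 months means calendar months and that no redacted footnote adds a later contact; the visible text has none. The count of under about 0.05 assumes that contraception continues as required. The documents give no pregnancy rate for women who stop it early, and the expected number rises in proportion to whatever rate is assumed. The half-lives come from single-dose or short-course Phase 1 studies and are assumed to hold after repeated dosing; the conclusion does not depend on them.

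**What to change.** Add to Section 6.3.1 and to the pregnancy-test footnotes of Table 4 (k), Table 5 (g) and Table 6 (g):

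*If the Final Safety Follow-up Visit takes place earlier than 5 months after the last dose of IP, FCBP will be contacted by telephone at 5 months (+ 7 days) after the last dose to ask about pregnancy and contraception or abstinence since that visit; a suspected pregnancy is handled per Section 10.4.1.*

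In criterion 7a, keep the existing endpoint for testing and add: *and to be contacted 5 months after the last dose of IP, if later*. This should be an addition. Replacing the endpoint with 5 months could shorten testing for women who stop treatment early but stay in the phase. Criterion 7b stays as it is. A self-reported home urine test at the call, and a matching change to the end-of-trial definition in Section 3.3, are optional.

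The cost is one call per FCBP who stops treatment, so at most 45, with no clinic visit. The last such contact would fall 38 to 41 days (about 6 weeks) after the last visit nominally, and at most 153 + 7 − 105 = 55 days after it with both windows. Section 9.1 ties the primary database lock to Week 48 or discontinuation and uses follow-up data available by then, so the primary analysis need not wait.
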